#### **6.11.6 Supplementary Analyses**

Analysis described in Section 6.11.2 will be repeated for the PP population.

Additional analysis will investigate the treatment effect on DSQ change from baseline in the subgroups defined in Section 5.9. This analysis will use ANCOVA similarly to the primary analysis (Section 6.11.2).

Empirical cumulative distribution function (eCDF) of the change from baseline in DSQ will be plotted by treatment group to demonstrate consistency of the treatment effect.

### **6.12 Analysis of Secondary Efficacy Endpoints**

#### **6.12.1 Percent Change in Tissue Eosinophil Count**

The percent change in peak esophageal intraepithelial eosinophil count at Week 24 will be analyzed using ANCOVA with treatment as a factor, baseline eosinophil counts and age strata as covariates. The LSM, SE, and 95% CI for individual treatment groups and the LSM, SE, 95% CI, and p-value for the between treatment difference will be presented.

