---	---

Target Disease Background and Rationale cont.
	
to 1 of 3 dose groups: placebo, low dose regimen (4 monthly doses of AK002 at 0.3, 1, 1, and 1 mg/kg), or high dose regimen (4 monthly doses of AK002 at 0.3, 1, 3, and 3 mg/kg). All primary and secondary endpoints were met.
 
There was a 97% and 92% mean reduction in eosinophils in the stomach and duodenum for the high dose group and low dose group, respectively, versus a 10% increase for placebo (p<0.0001). The reduction of eosinophils was associated with a statistically significant reduction in TSS8 of 58% in the high dose group, 49% in the low dose group, versus 24% reduction in the placebo group (p=0.0012).
 
Approximately 40% of subjects with EG and/or EoD in the Phase 2 study had concomitant EoE. Of these subjects with concomitant EoE, those treated with AK002 had a 95% mean reduction in eosinophil count in esophageal biopsies versus no change in subjects treated with placebo. The reduction of eosinophils was associated with a 53% reduction in dysphagia on AK002 versus 17% on placebo. In addition, 13 of the 14 EoE subjects receiving AK002 were histological responders (defined as ≤6 eosinophils/hpf) at Week 14.
 
By markedly reducing the number of blood and tissue eosinophils and inhibiting the activation of mast cells, AK002 may be useful in the treatment of patients with EoE. This Phase 2/3 study will evaluate the safety, tolerability, and clinical benefit of repeat doses of AK002 in adult and adolescent subjects with symptomatic EoE. Assessment of clinical benefit will include symptomatic, endoscopic, and histological improvement in disease.

Rationale for Dose Selection
	
Based on experience with AK002 in healthy volunteers and in subjects with ISM, chronic urticaria, severe AC, and EG and/or EoD, the proposed AK002 dose regimen of 6 total doses is 1 mg/kg for the first infusion, followed by either 1 mg/kg or 3 mg/kg administered every 4 weeks for 5 subsequent infusions. Subjects who complete randomized, double-blind, placebo-controlled treatment (all 6 doses of placebo or AK002) may have the option to receive 6 doses of open-label AK002 through participation in the Open-Label Extended Dosing (OLE) Period of the study.
 
CCI

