In the randomized, double-blind, placebo-controlled, Phase 2 study of AK002 in 65 subjects with EG and/or EoD, subjects were randomized to receive monthly doses of placebo, low dose AK002 (0.3, 1, 1, and 1 mg/kg), or high dose AK002 (0.3, 1, 3, and 3 mg/kg) in a 1:1:1 ratio. All primary and secondary endpoints were met in the study. There was a mean reduction of 97% and 92% in eosinophils in the stomach and duodenum at the high dose and low dose AK002-treated subjects, respectively, versus a 10% increase for placebo-treated subjects ($p < 0.0001$). The reduction of eosinophils was associated with a statistically significant reduction in total symptom score on 8 items (TSS8) of 58% in the high dose group, 49% in the low dose group versus 24% in the placebo group ($p = 0.0012$ and $p = 0.015$, respectively). Improvement in symptoms was observed within 24 hours of the first dose of study drug. In addition, 70% of high dose AK002-treated subjects and 68% of low dose AK002-treated subjects were treatment responders (defined as $>30\%$ improvement in TSS and $>75\%$ reduction from baseline in tissue eosinophils) versus 5% of placebo-treated subjects ($p < 0.0001$).

Approximately 40% of subjects had concomitant EoE. In those subjects, a mean reduction of 95% of eosinophils/hpf was observed in the esophageal biopsies of AK002-treated subjects versus no change on placebo. Also, 13 of 14 (93%) subjects with EoE on AK002 were histologic responders (defined by ≤ 6 eosinophils/hpf) versus 1 of 11 (9%) subjects with EoE on placebo. Dysphagia improved by 53% in AK002-treated subjects versus 17% in placebo-treated subjects.

AK002 was well tolerated with IRR being the only AE that occurred more frequently in AK002-treated subjects than in placebo-treated subjects.

More than 90% of subjects in the Phase 2 study elected to continue into a long-term continuation study. In the long-term, open-label continuation study, a starting dose of 1 mg/kg was used, followed by subsequent doses of 3 mg/kg. Premedication of 80 mg prednisone was administered the day before the first dose and second dose and, using this regimen, no IRR were reported for the first infusion of the continuation study.

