### 3.6 Determination of Sample Size

To achieve statistical significance for the first co-primary endpoint, a sample size of 8 subjects per treatment group will provide 90% power to demonstrate a statistically significant difference between AK002 and placebo in achieving the histological response (defined as the peak esophageal intraepithelial eosinophil count  $\leq 6$  cells/hpf) at Week 24. This calculation is based on the AK002-003 study in which 90% of AK002 subjects and 10% of placebo subjects achieved the histologic response at Day 99. The hypothesized treatment effect of 80% yielded a small number of subjects per group for the first co-primary endpoint.

To achieve statistical significance for the second co-primary endpoint, a sample size of 86 subjects per treatment group will provide 90% power to demonstrate a statistically significant difference between any AK002 dose group and placebo treatment group in mean absolute change in DSQ score from baseline to Weeks 23–24. This calculation is based on the baseline score of  $30 \pm 15$  (mean  $\pm$  Standard Deviation [SD]) reported in the literature, and an expected mean reduction of 15 in the AK002 group and 7.5 in the placebo group, and a SD of 15 for the change from baseline (Dellon, 2021; Hirano, 2019; Hudgens, 2017).

Consequently, approximately 100 subjects per treatment group will be included for a total of 300 subjects, driven by the second co-primary endpoint and a potential 14% dropout rate.

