Dates will be presented in the ISO-8601 format YYYY-MM-DD. Times will be displayed in 24-hour clock format. Numbering for tables, figures and listings will follow ICH E3 Guideline (ICH, 1996).

Alternative methods of analysis of the data may be considered prior to database lock should some of the assumptions underlying the proposed analyses not be met. Reason for departure from the planned methods will be documented as an amendment to the SAP or in the CSR.

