## 9.4 Appendix 4 Example SAS Codes

```
/** Multiple Imputation **/
proc mi data=DSQ seed=1357986420 nimpute=50 out=DSQ_IMPUTED1 ;
    by TRTMT ;
    class DISEASE_STRAT ;
    mcmc chain=multiple impute=full initial=em nbiter=200 niter=100 ;
var B_EOS DISEASE_STRAT B_DSQ DSQ_W01_02 DSQ_W03_04... DSQ_W21_22 DSQ_W23_24 ;
quit;
/** Recalculate change from baseline **/
data DSQ_imputed2;
    set DSQ_imputed1;
    chg=DSQ_w23_24 - b_DSQ;
run;

proc sort data=DSQ_imputed2 out=DSQ_imputed;
    by _imputation_;
run;

/** ANCOVA by imputation **/
ods output diffs=diffs lsmeans=lsmean;
proc mixed data=DSQ_imputed method=reml;
    by _imputation_;
    class TRTMT;
    model CHG=DISEASE_STRAT B_DSQ TRTMT;
    lsmeans TRTMT / diff;
quit;
ods output close;

/** Combine LS Means (by treatment and difference) **/
data lsmdiff;
    set lsm diffs(in=d);
    if d then trtmt='DIFF';
run;

proc sort;

    by trtmt;
run;

/** Synthesized results **/
ods output ParameterEstimates=SYNDIF;
proc mianalyze data=LSMDIFF alpha=0.05;
    by trtmt;
    modeleffects ESTIMATE;
    stderr;
run ;
ods output close;
```

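### SAP 6.12.1 gives percent change in eosinophil count an ordinary common-variance ANCOVA, although AK002 should vary far less than placebo, so the per-arm error bars, and in a three-arm fit those of the difference, would be wrong

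*SAP*

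**What the plan says.** SAP 6.12.1 states that the endpoint "will be analyzed using ANCOVA with treatment as a factor, baseline eosinophil counts and age strata as covariates". From that model it will present "The LSM, SE, and 95% CI for individual treatment groups and the LSM, SE, 95% CI, and p-value for the between treatment difference". It names no variance structure, robust standard error, transformation or rank method, and it does not say whether one model covers all three arms or each dose is fitted separately against placebo. Protocol 15.7.2 has the same kind of model with baseline DSQ added; the SAP supersedes it.

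The only ANCOVA code in the SAP is the DSQ example in Appendix 4. It fits all arms together with treatment as a class variable ("model CHG=DISEASE_STRAT B_DSQ TRTMT") and has no statement allowing the residual variance to differ by arm.

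The endpoint is formally tested against placebo at position 7 (high dose) and position 14 (low dose) of SAP Table 7.

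On what to expect, Protocol 2.3 reports that in Phase 2 subjects with concomitant EoE "a mean reduction of 95% of eosinophils/hpf was observed in the esophageal biopsies of AK002-treated subjects versus no change on placebo", and that "13 of 14 (93%) subjects with EoE on AK002 were histologic responders", against 1 of 11 on placebo. The histology sample size in SAP 3.6 assumes that "90% of AK002 subjects and 10% of placebo subjects achieved the histologic response at Day 99".

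SAP 5.1 has a general clause: "Alternative methods of analysis of the data may be considered prior to database lock", should assumptions fail. It sets no check or fallback for this endpoint.

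**The concern.** Percent change cannot fall below -100%. If AK002 averages about -95%, most of its subjects are pressed against that floor and their spread is limited. Placebo subjects, centred near zero, can move a long way in both directions. An ordinary ANCOVA replaces these unlike variances by one pooled value. With two low-variance arms and one high-variance arm, the pooled value is too small for placebo and too large for AK002. It is also too small for AK002 minus placebo, because two of the three arms that feed it are the quiet ones.

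At stake is the precision reported for a formally tested secondary endpoint. The placebo mean and, in a three-arm fit, the treatment difference would look more certain than they are. The AK002 means would look less certain, with limits that can fall below the possible range.

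**Working it through.** **The plan's own figures.** The plan gives no SD, SE or power for this endpoint. Arm size comes from the DSQ calculation in SAP 3.6, which reproduces: with a difference of 7.5 and an SD of 15, two-sided 0.05, the noncentral t gives power 0.8999 at 85 per group and 0.9032 at 86, and 86/(1 - 0.14) = 100. The ratios below need equal arms but do not depend on arm size.

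**Assumption.** Let r = SD(AK002)/SD(placebo), with both doses sharing one SD. I took placebo SD 40-100 and AK002 SD 5-30 percentage points, so r runs from 5/100 = 0.05 to 30/40 = 0.75.

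**Three-arm fit.** The pooled variance is SDp²(1 + 2r²)/3. The ratios of model SE to true SE are:

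- AK002 minus placebo: √[2(1 + 2r²)/(3(1 + r²))]
- placebo mean: √[(1 + 2r²)/3]
- AK002 mean: √[(1 + 2r²)/3]/r

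Coverage of a nominal 95% interval is 2Φ(1.96 × ratio) - 1.

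**Pairwise fit.** The pooled variance is SDp²(1 + r²)/2. The ratio is exactly 1 for the difference, √[(1 + r²)/2] for placebo, and that value divided by r for AK002.

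| r (example SDs, placebo/AK002) | Difference, 3-arm: ratio (coverage) | Placebo, 3-arm: ratio (coverage) | AK002, 3-arm: ratio | Placebo, pairwise: ratio | AK002, pairwise: ratio |
|---|---|---|---|---|---|
| 0.75 (40/30) | 0.952 (93.8%) | 0.842 (90.1%) | 1.12 | 0.884 | 1.18 |
| 0.50 (60/30) | 0.894 (92.0%) | 0.707 (83.4%) | 1.41 | 0.791 | 1.58 |
| 0.25 (80/20) | 0.840 (90.0%) | 0.612 (77.0%) | 2.45 | 0.729 | 2.92 |
| 0.10 (100/10) | 0.821 (89.2%) | 0.583 (74.7%) | 5.83 | 0.711 | 7.11 |
| 0.05 (100/5) | 0.818 (89.1%) | 0.579 (74.3%) | 11.6 | 0.708 | 14.2 |

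Worked line for r = 0.75: (1 + 2 × 0.5625)/3 = 0.708. Placebo ratio √0.708 = 0.842; AK002 ratio 0.842/0.75 = 1.12; difference ratio √(2 × 0.708/1.5625) = 0.952.

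**Simulation of the ANCOVA** (3,000 trials per scenario, 86 or 100 per arm, baseline count and age in the model). Responder rates were 90-97% on AK002 and 9-10% on placebo. The resulting SDs, which rest on assumed distributions, were about 49-81 on placebo and 20-39 on AK002.

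- Common variance, three arms: coverage 90-94% for the difference, 79-88% for the placebo mean, 98-100% for the AK002 mean.
- Pairwise fit: difference coverage about 94-95%.
- Robust (HC2) variance, three arms: difference coverage about 94-95%. With SDs of about 81 and 39 and 100 per arm, the mean SE rose from 7.88 to 8.84 (empirical 8.88) and coverage from 92.2% to 95.2%.
- Extreme case, 100% against 0% responders: 88-90% for the difference and 73-75% for placebo with the common variance.
- The AK002-placebo test was significant in every run. In the least favourable scenario the difference was 86.8 - 9.7 = 77.1 points against a mean model SE of 8.50, a ratio of about 9.

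**Impossible limits.** The pooled variance is at least SDp²/3. With 100 per arm and an AK002 mean of -95%, the lower limit passes -100% once 1.96 × SDp/(√3 × 10) exceeds 5. That happens for a placebo SD above about 44, however tight the AK002 data are.

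**The case against.** The strongest reply is that a reader might infer from 6.12.1 that the SAP prescribes one three-arm model with a common variance, when the section does not say so. The Appendix 4 code is labelled an example and is written for DSQ, and the SAP calls the comparisons for the histologic responder endpoint pairwise (6.11.1, 6.11.2). In a pairwise fit with equal arms the difference SE is essentially right. This stands, so the claim about the difference is conditional on the fit. It does not rescue the per-arm intervals that 6.12.1 promises: pairwise, the placebo SE is still 12-29% too small and the AK002 SE 1.2-14 times too large over the same SD range.

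A reader might also infer that difference coverage must be about 89-90%. That needs r of about 0.25 or less. With 10% non-responders on AK002, as the sample size assumes, its spread is not close to zero and the distortion of the difference is moderate.

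A reader might further infer that the tests at steps 7 and 14, or the type I error, are compromised. The documents do not support this. The planned effect is many standard errors wide, and if all arms shared one distribution they would share one variance, so this mechanism would not inflate the error rate. Histologic response is also tested by Fisher's exact test at three thresholds, with no variance assumption.

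Finally, SAP 5.1 allows other methods before lock. At that stage the treatment codes are sealed (SAP 5.6) and Day 169 counts are withheld from the sponsor (Protocol 10.3), so unequal spread by arm could not be seen in the data. It can be foreseen from Phase 2, however, so the SAP can be amended now without unblinded data. The clause permits that but does not do it.

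**Conclusion.** Wrong as written, for the error bars. The per-arm SEs and CIs would be miscalibrated under either fit: placebo too narrow, AK002 too wide. Under the three-arm fit, which is the natural reading because treatment is a single factor and the example code fits all arms together, the difference CI is too narrow as well.

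The direction follows from the floor at -100% and the documents' own Phase 2 results. The size rests on SDs that the documents do not give, on equal arms, and on a similar spread in the two doses. With the SDs assumed above, the three-arm distortion of the difference runs from slight (5%) to appreciable (18%); the placebo and AK002 intervals are hit harder. The consequence is for estimation and reporting, with no expected change in the hierarchy.

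**What to change.** State in SAP 6.12.1 that one model is fitted to all three arms. Give it a separate residual variance per arm (PROC MIXED with REPEATED / GROUP=treatment and Satterthwaite or Kenward-Roger degrees of freedom) or a robust variance. Take every LSM, difference, CI and p-value from that model.

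The cost is about one line of code and one or two SAP sentences, slightly fewer degrees of freedom, and a slightly wider CI for the difference.

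The change does not remove skew, and it does not guarantee AK002 limits above -100%. With an AK002 SD of 30 and 100 per arm the half-width is 1.96 × 30/10 = 5.9 points, so a mean of -95% still gives a lower limit near -101%. If that matters for reporting, a rank-based or log-ratio sensitivity analysis could be added.

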#### **6.12.2 Proportion of Subjects Achieving Peak Esophageal Intraepithelial Eosinophil Count of $\leq 1$ and $< 15$ Eosinophils/hpf at Week 24**

These 2 endpoints will be analyzed using Fisher's exact test similar to the analysis for the first co-primary endpoint (Section 6.11.1).

### 6.12.3 Proportion of Treatment Responders

Treatment responder is defined as >30% improvement in DSQ at Weeks 23–24 and a peak esophageal intraepithelial eosinophil count  $\leq 6$  cells/hpf at Week 24. This endpoint will be analyzed using Fisher’s exact test similar to Section 6.11.1.

### 6.12.4 Proportion of Subjects with >50% Improvement in DSQ from Baseline to Weeks 23–24

This endpoint will be analyzed using the CMH test stratified by the randomization stratification, age, and baseline DSQ factors.

### 6.12.5 Percent Change in DSQ from Baseline to Weeks 23–24

This endpoint will be analyzed using similar methods for the change in DSQ score as discussed in Section 6.11.4.

### 6.12.6 Change in Biweekly Mean DSQ Over Time

The data will be analyzed using the MMRM with age, treatment, week, and treatment-by-week interaction as fixed factors, baseline DSQ (continuous) as covariates, and subject as repeated measure unit over time. The model will use change from baseline in the biweekly DSQ from Weeks 1–2 through Week 23–24.

The model variance-covariance matrix will be unstructured. If the computation does not converge, the covariance matrix will take the form of Toeplitz, AR(1), and compound symmetry, whichever converges first. The improved Kenward-Rodger’s method (SAS KR2 option) will be used to derive the denominator degrees-of-freedom. The LSM and 95% CI for the between group difference (active dose vs. placebo) will be estimated using the simple contrast at each week.

A sample SAS code is provided as follows.

```
proc mixed data=ADEF method=REML ;  
  class TRTPN USUBJID WEEKS ;  
  model CHG = B_DSQ AGE_STRAT TRTPN WEEKS TRTPN*WEEKS / ddfm=KR2 ;  
  repeated WEEKS / subject=USUBJID(TRTPN) type=UN ;  
  lsmeans TRTPN*WEEKS / pdiff cl ;  
run ;
```

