Change in continuous outcomes will be analyzed using a mixed model for repeated measures (MMRM) and will include fixed effects for baseline value, treatment, week, and the treatment-by-week interaction and allow for random subject effects. Treatment and week will each be fitted as categorical variables. Model will assume unstructured covariance structure. If the model with unstructured covariance does not converge or it is determined to be inappropriate as outlined in the Guerin and Stroup study, (Guerin, 2000), then other covariance structures will be considered to model the within-subject errors. The selection of the covariance structure for the final model will be handled in a hierarchical fashion with the order being heterogeneous Toeplitz, AR(1), and compound symmetry, respectively. The Kenward-Rogers approach for computing denominator degrees of freedom will be used to account appropriately for pooling of within and between-subject variance estimates. The LSM with 95% CI will be presented for each treatment*week cross-classification.

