### 6.13 Analysis of Exploratory Endpoints

Change in continuous exploratory endpoints collected at multiple post-baseline time points will be analyzed using MMRM and will include fixed effects for age, baseline value, treatment, visit, and the treatment-by-visit interaction and allow for random subject effects. Treatment and week will each be fitted as categorical variables. The model will assume unstructured covariance structure.

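### The biweekly DSQ repeated-measures model forces one baseline slope on all 12 intervals, which can cost precision and add modest bias at Weeks 23–24

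*SAP*

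**What the plan says.** SAP 6.12.6 analyses change in biweekly DSQ with an "MMRM with age, treatment, week, and treatment-by-week interaction as fixed factors, baseline DSQ (continuous) as covariates". The sample program matches the text: "model CHG = B_DSQ AGE_STRAT TRTPN WEEKS TRTPN*WEEKS / ddfm=KR2". Treatment is crossed with week; baseline DSQ enters once. On the data used: "The model will use change from baseline in the biweekly DSQ from Weeks 1–2 through Week 23–24", which is 12 intervals. On covariance: "The model variance-covariance matrix will be unstructured", with simpler structures as fallbacks. The active-versus-placebo difference "will be estimated using the simple contrast at each week".

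No other section supplies the missing term. Protocol 15.7.1 lists "fixed effects for baseline value, treatment, week, and the treatment-by-week interaction". SAP 6.13 gives the exploratory models "fixed effects for age, baseline value, treatment, visit, and the treatment-by-visit interaction".

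In SAP Table 7 this model serves secondary endpoint 7, at step 15 (high dose) and step 16 (low dose) of 18. The co-primary DSQ comparison at Weeks 23–24 is a different analysis: ANCOVA (SAP 6.11.4) after multiple imputation run separately by arm, with baseline DSQ in the same multivariate distribution as every interval (SAP 5.4.2).

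**The concern.** Change from baseline is usually related to baseline, and the relation usually strengthens with time, because later scores correlate less with baseline than scores taken just after it. Weeks 1–2 directly follow the 14-day baseline window; Weeks 23–24 are almost half a year away. A single coefficient cannot be right at both ends if the slope drifts.

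With serially correlated scores the likelihood sets the common slope mainly by the early intervals, where baseline predicts the score best. Weeks 23–24 is then under-adjusted for baseline. An unstructured covariance recovers part of the lost information but does not correct the mean model.

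Two things are at stake. One is precision of the late-interval contrasts. The other is protection against dropout that depends on baseline, which a model containing baseline should give. Arm-specific missingness is not far-fetched. SAP 5.4.2 sets scores to missing after an intercurrent event, and SAP Appendix 2 counts both discontinuation for infusion reactions and events that reflect uncontrolled disease (rescue steroids, therapeutic endoscopy). The protocol synopsis reports infusion reactions as more frequent on active drug in the Phase 2 study.

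**Working it through.** **Inputs from the documents (SAP 3.6).** Baseline DSQ 30 with SD 15; "a SD of 15 for the change from baseline"; mean reductions of 15 and 7.5, so a difference of 7.5; 86 per arm for 90% power; 14% dropout; about 100 per arm.

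**The plan's own figure.** n = 2 × (1.960 + 1.282)² × 15² / 7.5² = 84.1, so 85 by the normal approximation and 86 by the noncentral t. Then 86 / (1 − 0.14) = 100. The planning figure reproduces. The planning standard error is 15 × √(2/86) = 2.29.

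**What the figures say about the late slope.** Let s be the SD of the Weeks 23–24 score, which is not given. From 15² = 15² + s² − 2·cov, cov = s²/2, and the slope of change on baseline is s²/450 − 1. For s = 15 this is −0.50 (correlation 0.50). It is −0.78 for s = 10 and −0.11 for s = 20. The documents give nothing on Weeks 1–2, so the early slope has to be assumed.

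**Precision.** Take s = 15. With a week-specific slope the Weeks 23–24 residual SD is 15 × √(1 − 0.5²) = 12.99. With a common slope b, the residual variance is about 12.99² + (b + 0.5)² × 15². Large simulated samples were fitted by maximum likelihood with an unstructured 12 × 12 covariance and an exponential decay in the baseline correlation:

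| Baseline correlation, Weeks 1–2 to 23–24 | Fitted common slope | Residual SD, week-specific | Residual SD, common | SE ratio | SE at 86 per arm, common | Power for 7.5 points |
|---|---|---|---|---|---|---|
| 0.50 throughout | −0.502 | 13.01 | 13.01 | 1.000 | 1.98 | 0.97 |
| 0.70 to 0.50 | −0.354 | 13.01 | 13.18 | 1.013 | 2.01 | 0.96 |
| 0.85 to 0.50 | −0.117 | 12.92 | 14.08 | 1.090 | 2.15 | 0.94 |
| 0.95 to 0.50 | 0.044 | 13.00 | 15.24 | 1.172 | 2.32 | 0.90 |

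Hand check of the third row: (−0.117 + 0.5)² × 225 = 33.0; √(168.75 + 33.0) = 14.2, close to 14.08. Across the other decay shapes and within-subject covariances tried, the increase was 4–9% from 0.85 and 11–17% from 0.95. The size also depends on s. From 0.85, the increase is 14% for s = 12 (final correlation 0.40) and 5% for s = 18 (final correlation 0.60).

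**Bias.** With 14% dropout per arm and log-odds of dropout of ±1 per baseline SD, common-slope and week-specific fits to the same data differed at Weeks 23–24 by:
- about 0.3–1.0 points for opposite directions by arm
- about 0.15–0.5 points for one arm only
- about 0 for the same direction in both arms

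Against 7.5 points, 0.15 is 2% and 1.0 is 13%. The sign depends on which arm loses its high-baseline subjects.

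**At trial size.** Three arms of 100, correlation 0.85 to 0.50, opposite dropout, 400 replicates: mean contrast −7.12 with the common slope and −7.63 with week-specific slopes (true value −7.5). The paired difference was 0.50 (Monte Carlo SE 0.04), and 0.50 / 7.5 = 7%. The empirical SD was 2.04 against 1.90, a ratio of 1.07.

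**Limits of the simulation.** It used maximum likelihood rather than REML with the planned degrees-of-freedom method, normal baselines without the entry cut at 12, simple randomization and no age term.

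**The case against.** The strongest reply is that nothing in the documents shows the slope to drift, and with a constant slope both effects are zero. That stands. A reader might infer from the SDs in SAP 3.6 that the plan's own figures prove unequal slopes. They do not: they bear on one late interval only, and even there the slope depends on an unstated follow-up SD. Features of the trial could also lower the Weeks 1–2 correlation, and with it the loss: a DSQ threshold for entry (regression to the mean), prednisone before the first dose, and the early symptom improvement reported in the Phase 2 study. The 0.95 starting point is therefore an upper case.

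A reader might also infer that any baseline-related dropout biases the contrast. It does not; the pattern must differ by arm. Nor is an inflated false-positive rate established. A simulation with no true effect gave 7–9% rejection against 6% with week-specific slopes, but it used z-tests and 240–1,000 replicates, so the Monte Carlo error near 6% is 0.75–1.5 percentage points.

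The stakes are also low. Endpoint 7 is reached only after 14 successful steps, and SAP 6.12.6 does not say which week's contrast decides it, so an effect on the gating of steps 17 and 18 cannot be read from the plan.

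The reply does not justify the restriction. The SAP gives no reason for it, and its own imputation model does not impose it.

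**Conclusion.** The restriction is certain; its consequences are conditional. If the relation of change to baseline differs between early and late intervals, the Weeks 23–24 contrast in 6.12.6 loses precision relative to a model with week-specific slopes: nothing with a constant slope, about 1% in standard error from 0.70, 4–9% from 0.85 and 11–17% from 0.95, each falling to 0.50. If baseline-related dropout also differs by arm, a bias of roughly 0.15 to 1.0 points can appear. The correlation paths and dropout slopes behind these figures are assumptions.

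It would be wrong to conclude that the trial is underpowered or that the co-primary DSQ result is at risk. Even the largest standard error in the table, 2.32, is about the planning value of 2.29, and the co-primary ANCOVA does not share the constraint. The point concerns endpoint 7, the by-week estimates and, by the same logic, the repeated-measures models of 6.13, for which no size was computed. It is an inexpensive improvement to a low-ranked but alpha-controlled analysis.

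**What to change.** Before unblinding, add the baseline-by-week interaction to the text of SAP 6.12.6 and append `B_DSQ*WEEKS` to the MODEL statement there. Add the matching baseline-by-visit term to the repeated-measures models of 6.13. In the same edit, name the week or contrast that decides endpoint 7 at steps 15 and 16.

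The interaction costs 12 − 1 = 11 degrees of freedom with about 300 subjects, plus one line of text and code. No new data are needed. If the slopes are in fact equal, almost nothing is lost. Made after unblinding, the same change would look data-driven.

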## 1. Introduction

This statistical analysis plan (SAP) describes the rules and conventions to be used in the analysis and presentation of efficacy and safety of AK002 in adult and adolescent subjects with active eosinophilic esophagitis (EoE) as planned for the clinical protocol.

The SAP describes the data and variables to be summarized or analyzed, including specifications of the analytical methods to be performed. This SAP supersedes the statistical analysis methods described in the clinical protocol except for the standard pharmacokinetics (PK) data analyses. Significant deviations/changes from the planned analyses described in this SAP will be identified, with justification, in the appropriate section of the clinical study report (CSR). The SAP is based on Clinical Study Protocol AK002-014 Amendment 6, dated 28 October 2021, and the associated electronic case report forms (eCRF).

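### If the unstructured MMRM for biweekly DSQ does not converge, the SAP's constant-variance fallbacks give wrong per-week standard errors whenever the variance of change differs over time; the protocol's heterogeneous Toeplitz has been dropped without explanation

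*SAP*

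**What the plan says.** SAP 6.12.6 analyses change in biweekly mean DSQ with an MMRM. On its time points it says: "The model will use change from baseline in the biweekly DSQ from Weeks 1–2 through Week 23–24". That is 12 repeated measures. On covariance it says "The model variance-covariance matrix will be unstructured", and on failure to converge, "the covariance matrix will take the form of Toeplitz, AR(1), and compound symmetry, whichever converges first". On inference it says "The improved Kenward-Rodger’s method (SAS KR2 option) will be used to derive the denominator degrees-of-freedom". No empirical (sandwich) standard error is named. The active-versus-placebo difference "will be estimated using the simple contrast at each week".

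Protocol 15.7.1 also starts from unstructured and then lists its fallbacks "with the order being heterogeneous Toeplitz, AR(1), and compound symmetry, respectively". The protocol synopsis gives the same order.

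SAP section 1 settles precedence: "This SAP supersedes the statistical analysis methods described in the clinical protocol except for the standard pharmacokinetics (PK) data analyses". The SAP list is therefore the operative one. In SAP Table 7 this endpoint is step 15 (high dose) and step 16 (low dose) of 18.

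**The concern.** A heterogeneous Toeplitz structure lets each interval have its own variance. Plain Toeplitz, AR(1) and compound symmetry do not: each has one variance parameter for all 12 intervals. Under any of them, the standard error of every weekly contrast comes from a variance pooled over Weeks 1–2 to Weeks 23–24. Kenward-Roger adjusts for the estimation of covariance parameters and for degrees of freedom. It does not repair a covariance structure of the wrong shape.

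The variance of a change score need not be constant over 24 weeks. It may grow as the correlation with baseline weakens, or shrink as scores approach the DSQ floor of 0. In either case some weekly intervals would be too narrow and others too wide. The protocol's first fallback avoided this and the SAP's does not. At stake are the reported weekly estimates and intervals for a late secondary endpoint, and only if the unstructured model, with 12 × 13 / 2 = 78 covariance parameters, fails to converge.

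**Working it through.** **Inputs from the documents.** SAP 3.6 gives "an expected mean reduction of 15 in the AK002 group and 7.5 in the placebo group, and a SD of 15 for the change from" the pre-treatment score, with 86 subjects per group, 90% power and 14% dropout. SAP 5.8 sets the two-sided level at 0.05. Neither document gives an SD of DSQ change for any interval before Weeks 23–24.

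**The plan's own figure.** n per group = (1.960 + 1.282)² × 2 × 15² / 7.5² = 84.06, so 85 by the normal approximation. At 86 per group, power is 90.6% (normal) or 90.3% (noncentral t). Allowing for dropout, 86 / 0.86 = 100. The sample size reproduces.

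**The correct standard error.** With complete data and a separate mean for each treatment and week, the estimated weekly difference does not depend on the covariance structure; only its stated standard error does. With 86 per group and SD 15 at Weeks 23–24, the true value is 15 × √(2/86) = 2.29. Unstructured and heterogeneous Toeplitz both recover this, whatever the earlier SDs are.

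**The constant-variance standard error.** I assumed SD paths that move linearly over 12 intervals and end at 15, with correlation 0.5 + 0.5 × 0.8^lag between intervals. The best-fitting (Kullback-Leibler) plain Toeplitz matrix was found for each path. Its fitted SD is close to the root mean square of the 12 SDs, so the ratio at Weeks 23–24 can be checked by hand: for 9 to 15, 12.15 / 15 = 0.81; for 12 to 15, 13.53 / 15 = 0.90. Coverage is 2Φ(1.96 × ratio) − 1.

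| SD path (assumed) | RMS SD | Fallback SE, Weeks 23–24 | Ratio to 2.29 | 95% CI coverage |
|---|---|---|---|---|
| 9 rising to 15 | 12.15 | 1.87 | 0.82 | 89% |
| 12 rising to 15 | 13.53 | 2.07 | 0.90 | 92% |
| 15 throughout | 15.00 | 2.29 | 1.00 | 95% |
| 18 falling to 15 | 16.53 | 2.52 | 1.10 | 97% |
| 20 falling to 15 | 17.57 | 2.69 | 1.17 | 98% |

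AR(1) and compound symmetry give nearly the same ratios (0.81 to 1.17 across the table). With 100 per group and 14% monotone dropout, the Toeplitz ratios are 0.81, 0.90, 1.00, 1.11 and 1.18. If the SD rises from 9 to 15 by Weeks 7–8 and then stays flat, the ratio is 0.90 to 0.94, depending on the structure.

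**The first interval errs the other way.** Using the RMS SD, the Weeks 1–2 ratio is 12.15 / 9 = 1.35 and 13.53 / 12 = 1.13 on the rising paths, and 16.53 / 18 = 0.92 and 17.57 / 20 = 0.88 on the falling ones.

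**Is a rise plausible?** If the DSQ SD were 15 at every interval, the variance of change would be 2 × 15² × (1 − r) = 450(1 − r), where r is the correlation with baseline. A change SD of 15 implies r = 0.50 at Weeks 23–24; starting SDs of 12 and 9 imply r = 0.68 and 0.82 at Weeks 1–2. That is reasonable but not documented. The SAP model also adjusts for baseline DSQ with one common slope. Working with the residual variance after that slope softens the two rising ratios to about 0.93 and 0.85.

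**The case against.** Five points weigh against giving this much importance.

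- **Direction.** A reader might infer that the Weeks 23–24 standard error will be too small. The documents do not support that. They give one SD of change and no path, and the floor at 0 together with baseline adjustment could produce flat or falling residual variance. This objection stands.
- **Type I error.** A reader might also infer that steps 15 and 16 run at 7.7% or 11%, the complements of 92% and 89% coverage. Those are sizes of a stand-alone test. Under SAP Table 7, steps 15 and 16 are reached only after steps 1 and 8 have rejected essentially the same Weeks 23–24 contrast by ANCOVA after multiple imputation (SAP 6.11.4), which does not use the MMRM covariance. A false rejection of that contrast at steps 15 or 16 is therefore bounded by the size of the tests at steps 1 and 8. The SAP also asks for a contrast at each week and names none as deciding these steps. This objection stands too.
- **Conditionality.** Nothing happens if the unstructured model converges, and there is no evidence that 78 parameters with about 300 subjects will fail. The SAP's trigger (non-convergence) is also narrower than the protocol's, which allows fallback if unstructured is judged inappropriate. This limits the importance of the point, but a fallback that is written down should still be sound.
- **Existing flexibility.** SAP 5.1 permits other methods before database lock if assumptions fail, with the reason documented. That permission does not correct the stated rule.
- **Scope of the remedy.** The protocol's second and third fallbacks, as written, are already constant-variance. Only the first step is a departure from the protocol; changing the later ones is an improvement, not a restoration.

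**Conclusion.** The discrepancy is certain, and its consequence is conditional. If the unstructured fit fails, each weekly contrast takes its standard error from one variance pooled over 12 intervals, and that standard error is wrong wherever the interval's variance differs from the pooled one. At Weeks 23–24 the error ranges from about 18% too small to about 17% too large over the assumed paths, and is zero if the SD is flat. These sizes rest on assumed linear SD paths and an assumed correlation pattern; only the end value of 15 comes from the SAP.

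The damage is confined to the accuracy of weekly standard errors and intervals for a late secondary endpoint. The co-primary DSQ analysis is untouched, and the documents do not support a claim of inflated hierarchy error for the Weeks 23–24 contrast. This is a minor point, worth correcting because the correction is cheap and works in either direction.

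**What to change.** In SAP 6.12.6, restore heterogeneous Toeplitz (TYPE=TOEPH) as the first fallback after unstructured, or state why it was dropped. Preferably make the later fallbacks heterogeneous as well, ARH(1) and then CSH, tried in that fixed order; this goes beyond the protocol's own second and third choices. If constant-variance AR(1) or compound symmetry is kept, an empirical standard error would protect the intervals, but the Kenward-Roger option would then have to be replaced.

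The cost is one sentence, amended before unblinding. Each heterogeneous form has 12 variances where the plain form has 1, so it adds 11 parameters to a fallback model fitted to about 300 subjects, which that sample can support. The change also removes the discrepancy between the protocol and the SAP on the first fallback.
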